5.7. XR-NTX Treatment in the Community

5.7.1. Glenwood Life Counseling Center for XR-NTX injections. The participants randomized to XR-NTX-OTx will go to GLCC only to receive injections under the direction of [name] and the study nurse from prison in order to ensure continuity of care for those receiving XR-NTX in the community (injections will occur every 28 days). The study RA will be in close contact upon release and will provide the client with reminder calls and/or visits prior to each XR-NTX appointment. Prior to each injection (at GLCC and place of residence), the nurse will administer: 1) a drug use questionnaire, and 2) an instant urine drug screening test. If negative for opioid use participants will be administered XR-NTX. If the participant reports using opioids in the past 7-10 days or tests positive on the urine drug screen they will not be administered XR-NTX (see procedures below for missed XR-NTX injections). Once the participant receives the injection, he/she will be monitored for up to 1½ hours. In addition, the nurse will provide the participant with the Naltrexone Medication Card, and tell the participant that he/she should keep it at all times. The nurse or physician will follow the same procedures as in prison.

5.7.2. Place of Residence for XR-NTX injections. For those randomized to receive XR-NTX at their place of residence, specific procedures will be implemented. First, the study nurse will be accompanied by the study RA so two staff members are always physically present. The study RA will confirm the place of residence prior to release from prison using our locator form. Contact will be made with the participant immediately following prison release and subsequently one week before each scheduled injection to verify his/her home address as

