
5.7.3. Missed XR-NTX Injections. Participants who miss a monthly appointment will be contacted by the study RA within 24 hours of missing their appointment. The participant will be strongly encouraged to receive their next injection. If they miss a dose and return for a subsequent dose more than 7 days after their missed scheduled injection they will receive the following: 1) drug use questionnaire; 2) urine rapid test; and 3) naloxone challenge before the naltrexone injection. Everyone who reports opioid use or has a positive urine test for opioids during days 29-37 will be given the naloxone test and then the oral naltrexone (12.5mg) prior to the Vivitrol injection. If a participant misses a scheduled injection, he/she will have up to 37 days to receive their next XR-NTX injection. We will also record the number of successful rescues and number of delayed returns to XR-NTX treatment. Participants will no longer receive XR-NTX if they become incarcerated in jail or prison (if incarcerated less than 37 days, they will still be eligible receive their injection).

5.7.4. Withdrawal from Naltrexone: Treatment Safety. Participants may voluntarily stop taking XR-NTX doses at any time without penalty. Naltrexone is an opioid antagonist with no opioid agonist properties and no withdrawal upon discontinuation. Potential side effects relate to the medication itself and to the injection. The most frequent side effects of the medication include opioid withdrawal symptoms for those participants who still have some trace of opioids in their system. There had been reports of increased liver enzymes in individuals receiving high doses of oral NTX in a study of obesity. For this reason, we have an exclusion criterion regarding elevated liver function tests at baseline. The injection can lead to local irritation, infection, and potentially abscesses, which in the most extreme circumstance may require surgical debridement. Participants receiving XR-NTX who require acute treatment of pain will be told that they need to inform their physicians that they are on XR-NTX because XR-NTX is an antagonist and will block the effects of opioid-agonist pain medications. In addition, each participant will also receive a laminated card that indicates they are on XR-NTX that can be provided to their health care provider.

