5.8. Measures

Assessment of participant characteristics and/or performance will involve a multidimensional set of instruments administered by trained research interviewers. See **Figure 2**, for a schematic of measures and when they are administered. Sources of information will include: (1) self-report; (2) official records; (3) urine drug screening results; and (4) treatment program records. Assessment at baseline will provide information on participant characteristics and pre-incarceration histories of substance use, substance use treatment, crime, incarceration, and HIV risk behavior. Participants in both conditions will be paid \$50 cash for each follow-up visit. Participants

will not be paid for baseline assessments in prison due to the fact that such payments may be viewed as coercion.

5.8.1. XR-NTX Adherence. Data on post-release treatment status will be obtained from GLCC records. Treatment status will be measured at each follow-up point by whether or not a participant received an injection of XR-NTX at each follow-up point (yes v. no). We will also collect data on whether a person entered outpatient treatment (yes v. no) and the type of services utilized. Treatment duration for individuals who end treatment will be calculated based on the last date of clinic attendance (if a participant fails to receive his/her injection by day 37 s/he would be considered a drop-out). Thirty seven days is used in our current XR-NTX studies as this is how long the medication typically protects the participant. We will also collect data on whether or not participants entered other types of treatment. Follow-up assessments will collect self-report data on reasons why participants entered, did not enter, or dropped out of treatment.

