9.1. Potential Risks

9.1.1. Extended-Release Naltrexone (XR-NTX). Participants may experience brief withdrawal symptoms with the naloxone test, although this will be uncommon as only patients with a history of no opiate use and negative urine for opiates will be given the test. Those receiving an XR-NTX intramuscular injection may experience side effects consisting of pain at the site of injection, nausea, or other opioid withdrawal symptoms. In rare cases, an infection at the site of injection has occurred. XR-NTX has been reported to cause increased liver enzymes when it was given in high dose oral form, but this has not been reported with the dose used in the injection. Participants in both conditions carry the risk of relapse to opioid dependence, as is the case for all individuals who have a history of opioid use disorder. Relapse to opioid dependence after a detoxification and opioid-free period, or after discontinuing depot naltrexone, carries a risk of opioid overdose and death because tolerance after a period of abstinence is low. Participants will be informed of these risks and of treatment alternatives, including agonist maintenance.

XR-NTX injections will block the effects of opioid pain medication and all participants randomized to the naltrexone condition will receive a card to present in case of emergency need for opioid analgesia. General anesthetics, nerve blocks, and non-steroidal pain medications are not affected. All individuals who will be administered depot naltrexone will be informed as follows: **“You should carry identification to alert medical personnel to the fact that you are taking depot naltrexone. A depot naltrexone medication card has been supplied to you for this purpose. Carrying the identification card should help to ensure that you can obtain adequate treatment in an emergency. If you require medical treatment, be sure to tell the treating physician that you are receiving depot naltrexone therapy”**.

9.1.2. Other Risks. Other risks are expected to be minimal. Participants will be asked to provide sensitive information regarding a number of behaviors, including deviant and criminal behaviors, and are thus exposed to the risks associated with the potential for disclosure of confidential information outside the research context. Because participants will be discussing personal information, including information on psychological functioning, some participants may experience emotional discomfort.

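### The naloxone-test rule after opioid use on days 29-37 contradicts the risk section, and the outcome of a positive screen and the return window are not fully defined

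*Combined protocol and SAP*

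**What the plan says.** **Who gets the naloxone test**
- 5.7.3 (missed injections): "Everyone who reports opioid use or has a positive urine test for opioids during days 29-37 will be given the naloxone test". Oral naltrexone follows, and both steps come before the injection.
- 9.1.1 (risks): "only patients with a history of no opiate use and negative urine for opiates will be given the test". This is the reason given for expecting withdrawal from the test to be uncommon.
- 5.6.2 (prison): the challenge is for participants who deny use in the previous 10 days and have a negative instant urine. Oral naltrexone follows only a negative challenge. 5.7.1 ends by applying the prison procedures in the community, and 5.7.2 applies the clinic procedures at the residence.

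**What follows a screen in the community**
- 5.7.1, negative: "If negative for opioid use participants will be administered XR-NTX".
- 5.7.1, reported use in the past 7-10 days or a positive screen: no injection, with a pointer to 5.7.3: "tests positive on the urine drug screen they will not be administered XR-NTX (see procedures below for missed XR-NTX injections".

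**Timing**
- 5.7.1: "injections will occur every 28 days".
- 5.7.3 sets a procedure (questionnaire, urine test, naloxone challenge) for those who "return for a subsequent dose more than 7 days after their missed scheduled injection". It then allows up to 37 days for the next injection, without saying from when.
- 5.7.3 also ends XR-NTX on incarceration, but keeps participants eligible if the incarceration is shorter than 37 days.
- 5.8.1: "if a participant fails to receive his/her injection by day 37 s/he would be considered a drop-out".

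**Coding**
- 5.8.1 scores adherence as injection received or not at each follow-up point, and takes treatment duration from the last clinic attendance. Figure 2 counts injections due and completed.

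**The concern.** Two things are at stake.

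The first is safety and disclosure. Section 9.1.1 supports its reassurance about withdrawal by saying who is tested. Section 5.7.3 sends to the test the very people whom 9.1.1 says are not tested. Section 5.7.4 itself links withdrawal symptoms to traces of opioids still in the system. The stated basis for the risk statement therefore does not hold for this part of the procedure.

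The second is coding. Adherence is outcome (a) of Aim 1, and months of post-release treatment is the exposure in Aim 2. Whether an injection may be given after a positive screen, and until which day a return counts, decides how many injections a participant can receive, when he or she becomes a drop-out, and how long treatment lasted. If the text leaves this open, staff will settle it visit by visit and the analyst will settle it again when coding.

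**Working it through.** There is no plan figure to reproduce. The check compares the passages and does day arithmetic on the plan's own numbers.

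**Step 1. Who is given the naloxone test?**

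| Section | Setting as written | Use reported or urine positive | No use and urine negative |
|---|---|---|---|
| 5.6.2 | Prison; carried to the community by 5.7.1 | Not tested | Tested |
| 5.7.3 | Community, days 29-37 | Tested | Tested if more than 7 days late |
| 9.1.1 | Not restricted | Not tested | Tested |

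The middle row cannot be reconciled with the other two for a participant with use or a positive urine. No cross-reference links 5.7.3 and 9.1.1.

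**Step 2. What follows a positive screen?** 5.7.1 withholds the injection and points to 5.7.3. 5.7.3 then gives the naloxone test and oral naltrexone before an injection. Read in sequence, this is withhold, then challenge. Two cases stay open:
- a participant who passes the challenge but whose urine is still positive, because no repeat negative urine is stated;
- a positive screen on day 28, the scheduled day, which falls before the range 29-37.

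**Step 3. Return window.** Inputs: interval 28 days (5.7.1), lateness trigger 7 days (5.7.3), limit 37 days (5.7.3 and 5.8.1).
- More than 7 days late: 28 + 7 = 35, so day 36 onward.
- Limit counted from the last injection: day 37, which is 37 − 28 = 9 days after the due date. This agrees with 5.8.1. The procedure for returns more than 7 days late then covers days 36 and 37 only.
- Limit counted from the missed appointment: 28 + 37 = day 65. An injection on days 38 to 65 would be inside the window of 5.7.3 but after drop-out under 5.8.1.

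**Step 4. Custody clause.** Take a participant jailed on day 10 for 30 days.
- Length of custody: 30 < 37, so still eligible under 5.7.3.
- Day of release: 10 + 30 = 40 > 37, so already a drop-out under 5.8.1.

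This conflict does not depend on where the 37-day window in Step 3 starts. Section 5.8.3 expects about 10% of participants to be re-incarcerated. Taken as a share of all 240, that is 0.10 × 240 = 24 people, but the documents do not say how many stays would be short.

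**Step 5. Scale, by assumption only.** The plan gives no rate of opioid-positive injection visits. Per arm, 120 × 6 = 720 community injections fall due. If 5% to 30% of these met reported use or a positive screen, and everyone passed both challenge steps, then 720 × 0.05 = 36 to 720 × 0.30 = 216 injections per arm (0.3 to 1.8 of 6 per participant) would switch between given and not given according to the reading. The 5% to 30% is assumed, and 720 ignores drop-out, so this is an upper range and not an estimate.

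**The case against.** The strongest defence has four parts.

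- **5.7.1 and 5.7.3 are linked.** A reader might infer that they flatly contradict each other, or that 5.7.3 injects everyone who is positive. The documents do not support either inference. 5.7.1 cross-refers to 5.7.3, and 5.6.2 gives oral naltrexone only after a negative challenge, so the challenge can be read as a condition for the injection. This stands. Only the two open cases in Step 2 remain.
- **The 37-day limits agree.** A reader might infer that 5.7.3 and 5.8.1 set different windows. They match if both count from the last injection. The range 29-37 and the rationale in 5.8.1, that protection typically lasts 37 days, favour that count. The sentence on returns more than 7 days late has no limit of its own, but the limit comes later in the same paragraph. This also stands, except that the starting point is unstated and the custody clause departs from 5.8.1. That clause might be meant to count from the last injection, which would remove the conflict, but as written it counts time incarcerated.
- **9.1.1 describes induction.** Its conditions match 5.6.2, and 9.2.1 speaks of screening potential participants. But 9.1.1 does not limit itself to the first injection, and no passage tells the reader that positive participants are tested later. 9.2.1 does disclose withdrawal from the challenge, which softens the gap without closing it.
- **Adherence records what happened.** A received injection is scored as received under any reading. That is right for the yes/no item. It does not settle whether the injection should have been given, or how drop-out and treatment duration are coded after day 37.

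**Conclusion.** The contradiction between 5.7.3 on one side and 9.1.1 and 5.6.2 on the other is firm. The remaining points are ambiguities, apart from the custody clause, which as worded conflicts with the drop-out rule in 5.8.1. The point should be fixed, but it does not by itself endanger the trial's conclusions.

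The size of any effect on adherence is unknown. A reader might infer from the pilot, where 10 of 27 received the fifth community injection, that affected visits will be common. That figure counts injections not received (27 − 10 = 17); it does not measure late or opioid-positive attendances, and Section 1.0 attributes many departures to housing, work, child care and supervision demands.

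A reader might also infer a bias between arms. The rules are written for the clinic and the residence alike, so none is built in. A bias would arise only if staff applied the rules differently by setting.

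The conclusion rests on taking 9.1.1 as unrestricted and the custody clause as counting days incarcerated, as both are worded. It takes no position on which clinical rule is right.

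**What to change.** The investigators should reconcile 5.6.2, 5.7.1, 5.7.3, 5.8.1 and 9.1.1 into one rule that states:

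1. who is given the naloxone test, in prison and in the community;
2. what follows reported use or a positive screen, including on the scheduled day and when the participant remains positive after the challenge;
3. the day from which the return window is counted and the day on which it ends, including after incarceration.

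The risk text should then describe the procedure actually used. The analysis section should code drop-out and treatment duration from the same rule in both arms, and say how an injection after the drop-out day is counted in Figure 2 and in Aim 2. The clinical content is for the investigators to decide.

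The cost is protocol wording, matching nurse forms and revised risk text. Sample size and data collection schedule do not change.

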5.8. Measures

Assessment of participant characteristics and/or performance will involve a multidimensional set of instruments administered by trained research interviewers. See **Figure 2**, for a schematic of measures and when they are administered. Sources of information will include: (1) self-report; (2) official records; (3) urine drug screening results; and (4) treatment program records. Assessment at baseline will provide information on participant characteristics and pre-incarceration histories of substance use, substance use treatment, crime, incarceration, and HIV risk behavior. Participants in both conditions will be paid \$50 cash for each follow-up visit. Participants

will not be paid for baseline assessments in prison due to the fact that such payments may be viewed as coercion.

5.8.1. XR-NTX Adherence. Data on post-release treatment status will be obtained from GLCC records. Treatment status will be measured at each follow-up point by whether or not a participant received an injection of XR-NTX at each follow-up point (yes v. no). We will also collect data on whether a person entered outpatient treatment (yes v. no) and the type of services utilized. Treatment duration for individuals who end treatment will be calculated based on the last date of clinic attendance (if a participant fails to receive his/her injection by day 37 s/he would be considered a drop-out). Thirty seven days is used in our current XR-NTX studies as this is how long the medication typically protects the participant. We will also collect data on whether or not participants entered other types of treatment. Follow-up assessments will collect self-report data on reasons why participants entered, did not enter, or dropped out of treatment.

5.8.2. Addiction Severity Index (ASI) with Timeline Follow-Back (TLFB). The ASI is a standardized 40-60 minute measure widely used in research to quantify problem areas in substance-using populations.^{89,90} This instrument has excellent inter-rater and test-retest reliability.^{89,90} We will also collect data on substance use frequency and criminal activity to cover the entirety of the follow-up periods post-baseline. In addition, we will use the DSM-5 opioid-related-disorder classification⁹¹ to assess opioid use severity (mild, moderate, severe). In addition to the ASI, we will collect baseline data on crime severity which is determined on the basis of a 7-point scale (a higher number indicating greater severity of criminal involvement) and classifies crime severity according to the most serious level of criminal activity in their lifetime prior to the index incarceration.⁹²

5.8.3. Biological Assays. Urine will be tested on-site with CLIA waived QuikScreen cups using an immunochromatographic assay for rapid (2-5 minute) qualitative results based on SAMHSA-standard cutoffs for alcohol (20mg/dl or 0.02% BAC), amphetamine/methamphetamine (1,000 ng/ml), cannabis (50 ng/ml), cocaine/ benzoylecgonine (150 ng/ml), and opiates/morphine (2000 ng/ml). In addition, we will test for methadone and buprenorphine, and for commonly abused prescription drugs (*oxycodone, hydrocodone, and codeine*) (100 ng/ml), and for *Fentanyl* (10ng/ml). Results will be used as outcome measures of heroin and other opioid use as well as to check on the validity of self-reported drug use information. Urine samples will not be obtained on the approximately 10% of participants who we expect to be re-incarcerated. Those participants in methadone or buprenorphine treatment who screen positive only on their respective treatment medication will be counted as negative for their urine drug screening results.

5.8.4. Risk Assessment of Battery (RAB). This self-administered questionnaire, designed to identify individuals engaging in acts that could transmit HIV and other infectious diseases,⁹³ contains 45-items consisting of three scales: a drug risk, sexual behavior risk, and an overall scale.

5.8.5. Opioid Overdose Scale. This self-administered questionnaire will ask participants to report the number of opiate overdoses where they did and did not receive medical attention. The questionnaire administered at baseline will cover the period prior to the instant incarceration while the questionnaire follow-up in the community, will cover post-release months 1-12.

5.8.6. Visual Analogue Scale (VAS). Participants are asked to place a mark across the line at the point that corresponds to their immediate craving for opioids. Anchors included 0 mm – ‘no cravings’ to 100 mm – ‘most

extreme cravings possible'.^{94,95} Participants will be assessed at baseline and at each follow-up visit and asked about peak cravings during the preceding 24 hours.

5.8.7. Health-related quality of life will be measured by the EuroQol 5D (EQ-5D).^{108, 109} The preference weights obtained from the EQ-5D will be used to calculate quality-adjusted life-years (QALYs; see section D.4). The EQ-5D is the most widely used generic, preference-based health-related quality of life instrument.¹¹⁰

5.8.8. Official Records. As in our previous research,⁹⁶ official record data will be obtained from the MDPSCS at 12-months. Data will include type (e.g., charges involved) and number of arrests, convictions, and incarcerations; and the number and length of time of each imposed disciplinary period. Criminal record data will be used to assess the validity of self-report criminal activity data.

5.8.9. Biometric Measures. All participants will complete the following biometric measures for inclusion/exclusion criteria, participant monitoring, and serious adverse event (SAE) and adverse event (AE) reporting. The following biometric measures will be completed (see **Figure 3**): 1) history and physical; 2) liver function tests (note: if a blood specimen is unable to be drawn the individual will not be excluded from participation), hepatitis profile; 3) vital signs; 4) concomitant medications; 5) pregnancy, 6) HIV; 7) Urine toxicology; and 8) AEs.

5.8.10. Data Management/Quality Control. Assessments will be administered by trained RAs, and closely supervised by the PI. RAs will receive training concerning: (a) initiating and developing rapport; (b) sensitivity regarding culture, gender, and sexual orientation; (c) forms administration; (d) serious adverse event reporting; (e) responsibility for maintaining participant confidentiality; and (f) follow-up procedures.

